Robotic-assisted benign hysterectomy – learning curve for surgeons and a randomized comparison of robotic single-site hysterectomy vs. multi-port laparoscopic hysterectomy

Background:

Robotic-assisted surgery in gynecology is one of the fastest growing fields of robotic surgery. In Denmark yearly 4000 hysterectomies are performed on benign indications (1) and minimal invasive technique used in hysterectomies has increased from 35 % to 80 %. These include vaginal, laparoscopic assisted and lately robotic-assisted hysterectomy. The robotic surgical system Da Vinci was introduced in 2000. By 2016, 3803 units were established worldwide and 644 of them in Europe. Hysterectomy and prostatectomy is by far the most common operations performed with the Da Vinci robot. Robotic-assisted surgery is an alternative to conventional laparoscopy allowing better ergonomy for the surgeon and precise movements due to endo-wristed instruments.

Robotic surgery in benign gynecology is still a matter of debate, due to expensive costs and lack of evidence of superiority to conventional laparoscopy regarding perisurgical outcome.

A new approach in hysterectomy is the robotic single-site technique (R-SS), which is based on one single incision compared to standard four incisions in multiport robotic- as well as conventional laparoscopy. This wound-sparring technique may reduce postoperative pain, allowing shorter hospitalization, shorter sick leave and better cosmesis. Since fast-track regimes are gaining ground in gynecology there is a need for detailed information about the new surgical technique, especially whether it can replace conventional multiport laparoscopy.

Determination of learning curves for a novel surgical technique like the robot provides valuable information regarding safety as well as applicability. For these reasons proper knowledge is important to which extent e.g. BMI, uterine size, and docking time at the robotic console influence the procedure. Secondly, the proper patient selection could be established for the various surgical options. To date, there are no detailed reports on robotic single-site hysterectomy using the newest robotic technology, the da Vinci, Xi system.

Multi-port versus Single-site in laparoscopic surgery

The advantage of laparoscopic hysterectomy compared to abdominal hysterectomy is associated to the lack of large abdominal wound, resulting in shortened hospitalization, faster postoperative recovery, and less postoperative pain(1) (Aarts, Nieboer et al. 2015) However, multiport laparoscopy is not without risks. A laparoscopic hysterectomy requires 4 trocar incisions, including muscles-splitting incisions. Reports suggest a 5% risk of neuropathic pain, as well as increased risk of infection and hernia at the trocar site (2) (Shin and Howard 2012).

In an attempt to improve the benefits of laparoscopic surgery, such as minimizing wound lesions as well as optimizing cosmetic results, the laparoscopic single-site technique was developed. This technique is based on one single multichannel device

placed through a 2 cm, relatively hidden, peri-umbilical skin incision. The device allows optics and multiple instruments access to the abdomen (Fig.1). A recent randomized study showed less bleeding (median 20 vs 50 ml) in robotic single port compared to laparoscopic multiport hysterectomy (3)(Paek et al 2016). In the largest randomized study to date Kim et al found transfusions rates were the most frequent complication required in 4.0% of single-port cases and 7.9% of multiport cases (3a) (Kim et al 2015). A review and metaanalysis comparing laparoscopic single-site with conventional multiport laparoscopic hysterectomy found that laparoscopic single-site was feasible and safe (4) (Sandberg, la Chapelle et al. 2017). There was no significant difference between the two techniques regarding complication rate, conversion risk and postoperative pain. However, the quality of evidence in the studies was low and various other observations like cosmesis was not consistently established.

Women's expectations; surgical safety and cosmesis

Surgical safety and cosmesis are important considerations for patients undergoing laparoscopy. A study by Golkar et al. (5) showed that preoperatively patients were mostly concerned about the surgical safety but, postoperatively, the patients mainly focused on the cosmetic result. Another prospective comparative study showed that the laparoscopic single-site incision was the preferred abdominal incision judged by questionnaire (6)(Yeung et al. 2013). Thus, there is a need for constantly improving and developing the end-points of care in our minimal invasive techniques.

Economic issues

Cost-analysis on R-SS compared to laparoscopic multiport hysterectomy in benign gynecology has a knowledge gap. A retrospective study suggests increased cost per case using R-SS compared to laparoscopic multiport hysterectomy (7)(El Hachem et al. 2016). A variety of circumstances influences the analyses such as already established infrastructure for robotic surgery at the hospital, high volume versus low volume robotic centers and experienced robotic teams. Cost-effectiveness analyses are essential in order to provide a responsible utilization of health care resources and includes determination on sick-leave, consultation to healthcare (ex kontakt I amb ell e.l. pga kir.relatedede problemstilling). If out-of-hospital costs are included these may vary between countries; however, the phase between hospital stay and return to work may imply extra cost for the patient, need for reimbursement from health insurances, visits to medical professionals due to related morbidity a.s.o. If rehabilitation with RSS is shorter and includes less extra medical cost and visits the total cost may be less.

Summary:

R-SS hysterectomy is a novel technique, which may be superior to conventional laparoscopic multiport hysterectomy in select patients regarding sick-leave, cosmesis and postoperative pain. We, therefore, aimed at evaluating the learning curve using different robotic equipment (DaVinci Si Multiport surgical system and DaVinci Xi multiport and single site surgical system) in our cohort since 2014 to determine its applicability in our hospital setting. Secondly, we perform a randomized trial to compare R-SS hysterectomy with conventional laparoscopic multiport hysterectomy with regard to outcome postoperative rehabilitation, cosmesis, and the operational cost

Aim of study

Our study aims to evaluate R-SS with respect to:

Primary outcome:

- Length of hospital stay and time to return to daily activities /work
- Cosmesis; pre-and postoperative evaluation
- Postoperative pain (VAS)

Secondary outcome

- Learning curve for robotic-assisted hysterectomy including R-SS hysterectomy
- Patient satisfaction with the cosmesis
- Duration of operation incl. detailed information of time consumption of defined steps at hysterectomy, operation- and console time, blood loss, conversion rates, additional ports, port-site hernias, time at hospital, re-admission
- Cost-effectiveness analysis for the R-SS hysterectomy

Materials and Methods

Study 1:

Detailed learning curves for robotic surgery- single site and multiport hysterectomy – a prospective, controlled study. A retrospective study of all robotic hysterectomy since 2014

The prospective controlled study compares R-SSH with robotic multiport hysterectomy (the controls) and will be performed at the Department of Gynecology, Herning Hospital, between September 2016 to end of December 2017. Sample size is estimated based on recommendations from the literature (8)(Cala V. et al. 2012). The study consists of two sub-studies (A and B). Each of the two sub-studies includes 40 procedures performed by two experienced laparoscopists with 20 procedures each.

A: Determination of learning curve for two similar experienced surgeons, for 40 robotic *multiport* hysterectomies – 20 hysterectomies per surgeon.

Inclusion criteria for the learning curve studies are hysterectomy on benign indication, ASA group 1 or 2, BMI (body mass in kg/heights in metres²) less than 35 kg/m² (for R-SS hysterectomy less than 30), uterine size less than 300 g estimated by ultrasound, using Ferraris formula.

Exclusion criteria are risk of adhesions, prior extensive abdominal surgery and prior midline incision, cutis laxa of abdomen surgery, endometriosis, and more than 1 cesarean section.

The procedure is video recorded and peri-and postoperative data are collected prospectively. Various steps during the procedure are determined such as various split time measurements like docking time, console time, vaginal cuff suturing, incision start, skin-to-skin and closure time. Uterine size and blood loss, as well as patient demographic data are registered.

B. The on-going study estimates the learning curve for *R-SS* hysterectomy. In- and exclusion criteria as for Study 1 except for inclusion criteria of BMI less than 30 kg/m²

C. Further, a retrospective cohort from the first robotic hysterectomies in 2014 until recently will be evaluated. The surgeries in the prospective studies are performed using the Da Vinci Xi surgical system and in the retrospective study using the Da Vinci Si Multiport system. Due to its design only crude incidences on perioperative variables will be evaluated.

Study 2

Robotic single-site hysterectomy compared to laparoscopic multiport hysterectomy – a prospective randomized controlled study; cosmetic satisfaction and surgical outcome.

The study is scheduled to start May 2018 and compares R-SS hysterectomy to laparoscopic multiport hysterectomy. Procedures are performed by an experienced three-surgeon team. Patients are randomized to either laparoscopic multiport hysterectomy (N=62) or R-SS hysterectomy (N=62) by random numbers in sealed envelopes prepared by a third party. Eligibility criteria are the same as for study 2B (i.e. BMI < 30 kg/m²). Patient's satisfaction with body image and cosmesis is assessed at different time points pre- and postoperatively by means of multidimensional body-self relations questionnaire – appearance evaluation sub-scale and POSAS. Postoperative pain and analgesia use will

be registered as well as secondary outcome parameters as described above. A follow-up at one, three, and six month include self evaluation of the scar and registration of port-site hernias, vaginal dehiscence or other complications (Vercellia et al). Interviews and diaries will include time of return to home and work, daily activities including sexuality

The R-SS hysterectomy is performed using da Vinci, Xi robotic system. One single port, diameter 2 cm is applied at the umbilicus. Applying an additional assistant port is defined as conversion of procedure

The laparoscopic multiport hysterectomy is performed using our standard equipment and 4 trocars, 5 mm each.

Study 3

Socio-economical consequences of R-SS hysterectomy versus conventional laparoscopic hysterectomy

Study details in preparation

Instrumental cost

Hospital stay

Post-hospitalization cost. sick days, extra visits to the out-patient clinic, general practitioner, medical expenses

Sample size calculation was based a PhD- study on fast track hysterectomy, which showed a difference in return to work of 4 days and SD ± 8 . 62 women in each group are needed for a power of 80% (beta=0.2) to replicate this study. To include those not working, we calculated that with an expected VAS of 0.86 ± 0.2 and 62 in each group the sample was sufficient to detect a difference of 0.1 in VAS; still, with a power of 80%. All calculations are based on two-sided testing with alpha = 0.05.

The retrospective study was approved by the Data Authority (no. 1-16-02-913-17). The randomized trial is registered at clinicaltrials.gov (NHS).

Statistics

For statistical calculations of proportions the χ^2 -test with Yates' correction for discontinuity or the Fisher's Exact-test was used. For continuous variables Student's t-test, Mann-Whitney's U -test, and Wilcoxon's Signed Rank test was used when appropriate.

Questionnaires with partial answers were included in the calculations, if possible. ANOVA and Kruskal Wallis' test was performed between group variables. Post-hoc test with Newman-Keul's test was performed between group pairs, if ANOVA was significant.

Repeated measurements were evaluated with 2-way ANOVA and surgical procedure as group variable with potential confounding variables like age, BMI, surgeon, and additional surgery added. The distribution of BMI, age, blood loss, split times during operation, hospital stay and time of return to daily activities and work were evaluated by means of Kaplan-Meyer analysis. The level of significance was a two-sided $p < 0.05$. Logistics regression analysis was performed with surgical procedure as dependent variable and the various split times, surgeon, age, BMI, parity, as independent variables. Learning curves were established for each individual surgeon, surgical procedures, and combined

monitored over time of the studies. Data are given as mean \pm SD if following Gaussian distribution and median (minimum, maximum) if non-Gaussian distributed. IBM SPSS Statistics 20 was used as the statistical software

Research plan

Study 1; jan 2017-june 2018

Study 2; may. 2018-jan. 2020

Study 3; 2020-2021

Responsibility:

[name] [name], [name]. Department of Gynecology and Obstetrics, Herning Hospital, Principal data supervisor and investigator for clinicaltrials.gov
[name], Ph.D. Department of Gynecology and Obstetrics, Herning Hospital

References

El Hachem, L., et al. (2016). "Robotic Single-Site and Conventional Laparoscopic Surgery in Gynecology: Clinical Outcomes and Cost Analysis of a Matched Case-Control Study." *J Minim Invasive Gynecol* **23**(5): 760-768.

Golkar, F. C., et al. (2012). "Patients' perceptions of laparoendoscopic single-site surgery: the cosmetic effect." *Am J Surg* **204**(5): 751-761.

Sandberg, E. M., et al. (2017). "Laparoendoscopic single-site surgery versus conventional laparoscopy for hysterectomy: a systematic review and meta-analysis." *Arch Gynecol Obstet* **295**(5): 1089-1103.

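### Study 2 has at least four unranked primary outcomes, each tested at two-sided 0.05, and no rule for what counts as success

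*Protocol*

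**What the plan says.** The Aim of study section gives one primary outcome list for the whole project, in three bullets: "Length of hospital stay and time to return to daily activities /work", "Cosmesis; pre-and postoperative evaluation", and postoperative pain on a VAS.

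These are the randomized trial's outcomes. The Summary states that "we perform a randomized trial to compare R-SS hysterectomy with conventional laparoscopic multiport hysterectomy with regard to outcome postoperative rehabilitation, cosmesis" and operational cost. The Study 2 section collects cosmesis and pain, and adds "Interviews and diaries will include time of return to home and work, daily activities including sexuality". The learning curve, which is Study 1's subject, is listed as secondary.

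The sample size paragraph (printed after Study 3) starts from a fast-track study "which showed a difference in return to work of 4 days" with SD 8, giving 62 women per group. It then adds a VAS calculation so that women who do not work are covered. Both use two-sided 0.05 and 80% power. Hospital stay, return to daily activities and cosmesis have no calculation.

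The Statistics section sets a single two-sided 0.05 level. It treats hospital stay and return to daily activities and work as quantities to be analysed. The only multiplicity method it names is Newman-Keuls, for pairs of groups after a significant ANOVA.

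The secondary list repeats part of the primary list. It contains "port-site hernias, time at hospital, re-admission", so hospital stay appears at both levels. It also contains "Patient satisfaction with the cosmesis", which may or may not be a different measure from primary cosmesis.

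**The concern.** A 0.05 level controls the error of one test. With several primary outcomes, no order among them and no statement of which must be significant, any one of them could be reported as the positive primary result. The error rate of the trial's main conclusion is then not 5%.

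Newman-Keuls does not help. It handles several groups on one outcome, whereas Study 2 has two groups and several outcomes.

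The sample size paragraph does not settle the matter either. It sizes two outcomes and calls neither the lead.

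At stake is whether a possibly costlier robotic technique is judged better than standard laparoscopy. The Protocol's own background cites expense and a lack of evidence of superiority as the open questions.

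**Working it through.** **Inputs from the Protocol.** Two-sided alpha 0.05; 62 per group; return to work difference 4 days, SD 8; VAS difference 0.1, SD 0.2. Both standardized effects are d = 4/8 = 0.1/0.2 = 0.5.

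**Inputs assumed.** The Protocol gives no correlations and no success rule. I assume that any one significant outcome counts as success and that all outcomes share a common correlation ρ of 0, 0.3, 0.5 or 0.7.

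**Step 1: the plan's own figure.** By the normal approximation, n per group = 2(1.96 + 0.8416)²/0.5² = 62.8, so 63; power at 62 is 79.5%. A t-test gives 64 per group and 78.9% at 62. The stated 62 is reproduced closely enough, for each of the two outcomes taken alone at the full 0.05.

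**Step 2: number of outcomes, k.**
- k = 3: one per bullet.
- k = 4: hospital stay, return to daily activities/work, cosmesis, VAS pain.
- k = 5: daily activities and work counted separately.

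Cosmesis uses two instruments at several time points, so k could be larger still.

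**Step 3: chance of at least one false positive, either direction.** For ρ = 0 it is 1 − 0.95^k. For ρ > 0 it comes from numerical integration of equicorrelated normal statistics at the 1.96 limit.

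| k | ρ = 0 | 0.3 | 0.5 | 0.7 |
|---|---|---|---|---|
| 3 | 14.3% | 13.6% | 12.5% | 10.9% |
| 4 | 18.5% | 17.4% | 15.6% | 13.0% |
| 5 | 22.6% | 20.9% | 18.3% | 14.8% |

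The reference value is 5%.

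**Step 4: false positive favouring the robotic arm.** For ρ = 0 it is 1 − 0.975^k; the reference value is 2.5%.

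| k | ρ = 0 | 0.3 | 0.5 | 0.7 |
|---|---|---|---|---|
| 3 | 7.3% | 6.8% | 6.3% | 5.5% |
| 4 | 9.6% | 8.7% | 7.8% | 6.5% |
| 5 | 11.9% | 10.5% | 9.2% | 7.4% |

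**Step 5: power under the possible remedies (t-test, d = 0.5).**
- One primary at 0.05: 78.9% with 62 per group, 74.6% with 56, 69.7% with 50. For return to work, 56 and 50 correspond to an assumed 90% and 80% of women working.
- Fixed order, return to work then VAS, both effects real: VAS is reached and significant with probability 62 / 65 / 67% at ρ = 0 / 0.3 / 0.5 if all women work, and 55 / 58 / 60% with 50 working per group (simulation).
- Holm over four outcomes, 62 per group (simulation, unsized outcomes taken as null): 60% for a sized outcome if only that effect is real, 62 to 63% if both are. At least one of the two is detected with probability 84 / 79 / 76% at ρ = 0 / 0.3 / 0.5, and about 73% at ρ = 0.7.
- Holm over five outcomes: 57 to 59% for each, and 81 / 77 / 74% for at least one.
- First Holm step over four (alpha 0.0125) with only 50 working per group: 48.5% for return to work.

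**The case against.** The strongest reply is that the analysis plan is not shown. Testing orders, Holm procedures and success rules commonly sit there, and such a plan could rank these outcomes, or require all of them, without touching the Protocol's list. That is true of the testing procedure. It does not answer the narrower point: the Protocol itself fixes which outcomes are primary, makes several of them primary without rank, places hospital stay at both levels, and sets a flat 0.05.

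A second reply is that the inflation is conditional. The Protocol never says that any one outcome suffices. This stands as a qualification, and the figures are labelled accordingly. But the Protocol excludes no reading, and the open choice is the defect.

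Third, the 11% floor comes from three outcomes, while the list holds at least four. This is fair, and it makes the range cautious: with four outcomes the floor is 13.0%. Likewise, for a wrong claim that the robotic arm is better, the relevant figures are the one-directional ones against 2.5%.

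Fourth, preferring the sized outcomes as primary is a judgement. Study 2's own title stresses cosmetic satisfaction, so the investigators could defend cosmesis. They would then need a sample size calculation for it, which the Protocol lacks.

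Finally, the Holm power figures depend on taking the unsized outcomes as null. If all four effects were real at d = 0.5, power for each would be about 70%.

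**Conclusion.** The concern holds and must be fixed. As written, the Protocol does not hold the error of Study 2's main conclusion at 5%. If any one significant outcome counts, the probability of a false positive primary result is 10.9 to 14.3% with three outcomes, 13.0 to 18.5% with four and 14.8 to 22.6% with five. In each range the lower end assumes a common correlation of 0.7 and the upper end independence. If all outcomes had to be significant there would be no inflation, but power would fall below the planned 80%. Confidence is high: the list, the flat level and the absence of a ranking can be read directly, and only the size depends on the assumptions.

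**What to change.** **Main change.** For Study 2, name one primary outcome from the two already sized: time to return to work, or VAS pain at one named time if every woman must contribute. Test it at two-sided 0.05. List the other sized outcome, hospital stay, return to daily activities and cosmesis once each as secondary, and state whether satisfaction with cosmesis is a separate measure. Make the change by dated protocol amendment and registry update before any comparative results are seen.

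**If several must stay primary.** Prespecify in the same amendment a procedure covering all of them. One option is a fixed order that stops at the first non-significant result, for example return to work, VAS pain, return to daily activities, cosmesis (one named instrument, one named visit), hospital stay. The order is for the investigators to justify. The other option is Holm over the same list. A fixed order keeps the full 0.05 for the first test; Holm does not let one failed outcome block the rest.

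**Cost.** Naming one primary needs no extra patients, but fewer outcomes can be claimed as primary results. Return to work is informed only by women who work, so its power falls to about 75% or 70% if 90% or 80% do. Keeping several primaries costs the power shown in step 5: roughly 60% per sized outcome under Holm over four, or a 55 to 67% chance of reaching and showing the second outcome in a fixed order.

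**If comparative results have already been seen.** The ranking can no longer be prespecified. Report all the listed outcomes together, say that no lead was named, and do not present a single significant one as the trial's primary result.

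### Cheap improvement: one preoperative pain VAS, used as a covariate, could sharpen the primary pain comparison, by an amount the protocol's figures cannot settle

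*Protocol*

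**What the plan says.** Under Aim of study, the protocol names three primary-outcome bullets. The cosmesis bullet reads "Cosmesis; pre-and postoperative evaluation". The pain bullet reads "Postoperative pain (VAS").

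The Study 2 section keeps the same contrast. On cosmesis: "Patient's satisfaction with body image and cosmesis is assessed at different time points pre- and postoperatively", by questionnaire. On pain: "Postoperative pain and analgesia use will" be registered. No preoperative pain score is mentioned for the randomized study, and none is ruled out. No time point is given for the postoperative VAS.

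The sample-size paragraph (under Study 3) relies on pain as well as return to work. It gives an "expected VAS of 0.86 ± 0.2 and 62 in each group the sample was sufficient to detect a difference of 0.1 in VAS", with 80% power, and adds: "All calculations are based on two-sided testing with alpha = 0.05". It introduces this calculation as a way to include women who do not work, but the figure of 62 per group is the whole arm.

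The Statistics section plans a two-way ANOVA for repeated measurements. It gives age, BMI, surgeon and additional surgery as examples of added variables. Baseline pain is not among the examples, but the list is open.

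**The concern.** Women differ in the pain they have before surgery and in how they use a VAS. If either carries over into the postoperative score, it adds to the spread within each arm, and a preoperative score used as a covariate would remove part of it. Women already have a preoperative assessment, so the score looks nearly free to collect.

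Two things make the point worth raising in the protocol. First, it concerns data collection: an analysis plan may choose covariates, but it cannot adjust for a score that nobody recorded. Second, the pain calculation has no slack. The number randomized equals the number calculated, with no stated allowance for loss. What is at stake is precision in one primary comparison. Validity is not in question.

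**Working it through.** **Inputs from the protocol.** VAS difference 0.1, SD 0.2, 62 per arm, 1:1 allocation, two-sided alpha 0.05, target power 80% (sample-size paragraph and Study 2).

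**Input assumed.** The correlation r between preoperative and postoperative VAS. The protocol gives none, so I use 0.1 to 0.5.

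**Step 1: reproduce the plan's figure.** The standardized difference is 0.1/0.2 = 0.5. By the normal approximation, n per arm = 2 × (1.960 + 0.842)² / 0.5² = 62.8, so 63. The t-test version gives 63.8, so 64. Power at 62 per arm is 79.5% by the normal approximation and 78.9% by the noncentral t. The stated 62 and 80% therefore reproduce to within rounding, with no baseline measurement. Return to work (4 days, SD 8) has the same standardized difference, 4/8 = 0.5.

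**Step 2: add the baseline as a covariate (ANCOVA).** The formulas are:
- residual SD = 0.2 × √(1 − r²)
- effective standardized difference = 0.5 / √(1 − r²)
- equivalent unadjusted sample size = 62 / (1 − r²)

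Power is from the noncentral t at 62 per arm. Removing the one degree of freedom used by the covariate changes it by about 0.01 percentage point.

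| Assumed r | Variance reduction r² | Residual SD | Effective difference | Power | Equivalent n per arm |
|---|---|---|---|---|---|
| 0 (no baseline) | 0% | 0.200 | 0.500 | 78.9% | 62 |
| 0.1 | 1% | 0.199 | 0.503 | 79.3% | 62.6 |
| 0.2 | 4% | 0.196 | 0.510 | 80.5% | 64.6 |
| 0.3 | 9% | 0.191 | 0.524 | 82.5% | 68.1 |
| 0.4 | 16% | 0.183 | 0.546 | 85.4% | 73.8 |
| 0.5 | 25% | 0.173 | 0.577 | 89.0% | 82.7 |

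The gain is 0.4 percentage points at r = 0.1, 1.6 at 0.2, 3.6 at 0.3, 6.5 at 0.4 and about 10 at 0.5.

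**Step 3: why a covariate and not a change score.** With equal SDs before and after surgery (an assumption), the SD of the change is 0.2 × √(2(1 − r)). At r = 0.3 this is 0.2 × √1.4 = 0.237, larger than the 0.200 of the postoperative score alone. The two are equal at r = 0.5. Below that, a change score loses precision.

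**Step 4: effect of some loss.** If 59 per arm were analysed (about 5% lost, an assumption), power is 76.8% unadjusted and 80.6% with the covariate at r = 0.3.

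**The case against.** The strongest reply is that nothing here is wrong. Randomization makes the postoperative comparison unbiased, and the stated sample size reproduces without a baseline. Almost any trial could be told to add a covariate. This stands, and it is why the point is offered only as an improvement.

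A second reply is that the two outcomes differ in kind. Body image exists before surgery, whereas the Background presents the single-site technique as sparing wounds and so perhaps reducing postoperative pain. New wound pain has no true preoperative counterpart, and a baseline VAS would mostly record symptoms of the underlying condition. This also stands: treating pain and cosmesis differently is not an inconsistency. It is also a reason to expect a low r, as is the exclusion of endometriosis.

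A third reply is that r cannot be narrowed, because the protocol does not say when the VAS is taken. Correlation with baseline could differ greatly between the first hours under analgesia and a later follow-up. In addition, if VAS is analysed in the planned ANOVA with other covariates, the relevant gain is the increment over that model, which cannot be calculated from the protocol. Both parts stand.

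A reader might draw four stronger conclusions that the protocol does not support:
- **That precision is certainly being given up.** This depends wholly on r; near 0.1 the gain is practically nil.
- **That a preoperative VAS has been excluded.** The protocol is silent; it names only postoperative pain in both places and rules nothing out.
- **That the pain calculation protects power among women who do not work.** It uses all 62 per group and is not a calculation for that subgroup.
- **That the existing preoperative questionnaire already precedes randomization.** The Study 2 section says only that it "is assessed at different time points pre- and postoperatively". If it were completed after allocation was known, a self-reported pain baseline could be affected by that knowledge.

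What survives is that the cost is very small, essentially no precision is lost if r is near zero, and the choice cannot be made later.

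**Conclusion.** The point holds as an optional, low-cost improvement. It is neither an error nor a source of bias. Pain is a primary outcome and supports the sample size for all women, and the protocol describes no preoperative pain score although a preoperative assessment exists.

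Over assumed correlations of 0.1 to 0.5, the covariate would raise power at 62 per arm from 78.9% to between 79.3% and 89.0%. The lower part of that range is plausible; nothing in the protocol supports the upper part in particular. The figures rest on the protocol's SD of 0.2 and difference of 0.1, a single postoperative VAS compared by ANCOVA with no other covariates, complete data, and an r that is assumed throughout. Confidence in a worthwhile gain is low; confidence that the change would do no material harm to precision is high.

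**What to change.** Add one pain VAS to the preoperative assessment in Study 2, and state that it is completed before the allocation envelope is opened. State that it enters the arm comparison of postoperative VAS as a covariate, by analysis of covariance (on ranks if the scores are skewed), and not as a change score.

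The cost is one extra line on a form, one covariate in the model, and an occasional missing baseline value. If the preoperative questionnaire is currently given after allocation, the VAS would have to be taken earlier. A by-product is that the report could describe existing pain by arm and separate it from pain after the operation. The sample size need not change, and no gain should be claimed in advance, since r is unknown.

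### Only two surgeons have a documented robotic single-site series, yet three operate in the randomised trial, and neither allocation nor the recovery comparisons account for surgeon

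*Protocol*

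**What the plan says.** **Study 1 (learning curves).** "Each of the two sub-studies includes 40 procedures performed by two experienced laparoscopists with 20 procedures each". Sub-study A is robotic multiport and sub-study B is R-SS: "The on-going study estimates the learning curve for *R-SS* hysterectomy". The experience attributed to these two surgeons is in laparoscopy.

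**Study 2 (randomised trial).** "Procedures are performed by an experienced three-surgeon team", and "Patients are randomized to either laparoscopic multiport hysterectomy (N=62) or R-SS hysterectomy (N=62) by random numbers in sealed envelopes". No stratification by surgeon, division of cases or R-SS experience is stated.

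**The two techniques.** The Summary states: "R-SS hysterectomy is a novel technique, which may be superior to conventional laparoscopic multiport hysterectomy in select patients". Of the comparator, Study 2 states: "The laparoscopic multiport hysterectomy is performed using our standard equipment and 4 trocars, 5 mm each".

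**Statistics.** Surgeon appears as a possible confounder in the repeated-measures ANOVA, and as an independent variable in a logistic regression whose dependent variable is the operation performed. Learning curves are followed per surgeon and per procedure over the studies. Hospital stay and return to activities and work are assigned to Kaplan-Meier analysis, with t-tests and Mann-Whitney tests named for continuous variables in general.

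**Calendar.** Study 1 in Materials and Methods runs from September 2016 to the end of December 2017. The Research plan gives "Study 1; jan 2017-june 2018". Study 2 starts in May 2018 in both places.

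**The concern.** The protocol treats R-SS as a technique that has to be learned, then compares it with laparoscopy done on the department's usual equipment. If the surgeons differ in R-SS experience, part of the R-SS arm may be early cases while the laparoscopic arm has no such cases. A null result on recovery or pain would then be hard to tell apart from incomplete learning.

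A second risk comes from the allocation. The envelopes are not arranged by surgeon, and nothing says the operator is fixed before an envelope is opened. The surgeon mix may therefore differ between arms, by chance or because cases are assigned once the allocation is known. Either would mix a surgeon effect into the comparison of techniques. The protocol itself regards surgeon as a possible confounder but does not control for it in the design.

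**Working it through.** **1. The plan's own figure.** Inputs from the sample size paragraph (printed under Study 3): a gain of 4 days in return to work, SD 8, two-sided alpha 0.05, power 80%.

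n per group = 2 × (1.960 + 0.842)² × 8² / 4² = 62.8, so 63. A t-test calculation gives 64. The stated 62 is within two of both. Power at 62 per group is 79.5% by normal approximation and 78.9% by t-test. The figure reproduces.

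**2. Share of R-SS cases without a documented series.** Three surgeons in Study 2, two with an R-SS series in Study 1B. Assume that those two are in the team, that the third has no other R-SS experience, and that cases are split equally: 62 / 3 = 20.7, about 21 cases, or 33%.

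This is an expectation and not a limit. If each R-SS case fell at random to one of the three, the 95% range would be 14 to 28 cases (14/62 = 23% to 28/62 = 45%). The share is zero if the third surgeon learned R-SS elsewhere or performs no R-SS. It exceeds a third if the Study 1 surgeons are not all in the team, if the split is unequal, or if Study 1B is unfinished when randomisation starts.

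**3. What a surgeon main effect does.** Take equal thirds, balanced 1:1 within each surgeon, and let one surgeon's R-SS patients lose L days of the 4-day benefit. The within-surgeon differences are 4, 4 and 4 − L. The surgeon-adjusted difference is their average, 4 − L/3, which is also the unadjusted difference. The covariate removes nothing. Only a look by surgeon and case order can show the effect.

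**4. Illustration of size.** L is assumed; the protocol gives no value. Power is by normal approximation at 62 per group and SD 8.

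| Benefit lost in one third of R-SS cases | Expected difference (days) | Power |
|---|---|---|
| none (L = 0) | 4.00 | 79.5% |
| half (L = 2) | 4 − 2/3 = 3.33 | 64% |
| all (L = 4) | 4 − 4/3 = 2.67 | 46% |

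**5. Where surgeon enters the stated analysis.**
- Repeated-measures ANOVA: yes, as a main effect. Hospital stay and return to work are one value per woman and do not fall under it.
- Logistic regression: yes, but with the operation as the outcome. It can show whether surgeon is associated with arm; it gives no surgeon-adjusted treatment effect.
- t-test, Mann-Whitney, Kaplan-Meier: no surgeon term.

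**6. Dates.** With December 2017 as the end, Study 1 closes before Study 2 opens in May 2018. With June 2018, the two overlap in May and June 2018.

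**The case against.** The strongest reply is that this rests on silence. The team is called experienced, no member is described as a newcomer, and robotic hysterectomy has been done in the department since 2014. That reply stands as far as it goes: a reader might infer that the third surgeon is untrained in R-SS, and the protocol does not say so. It does not supply the missing information either. The technique is not named, and the retrospective series from 2014 used the Si multiport system, so it documents no R-SS experience.

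The power figures are also open to attack. A reader might infer that power falls to 46%. That would need the whole benefit to vanish in every one of about 21 cases, including the last. The protocol measures learning mainly by split times and does not link case number to recovery, and it attributes the hoped-for benefit to having one incision. The figures are illustrations only.

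A reader might also take 20 cases as a proficiency threshold. The protocol gives it as a study size, so it does not support an entry rule.

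On dates, June 2018 may cover analysis or the retrospective part, so the mismatch does not show unfinished training. That surgeons would be chosen after the envelope is opened is likewise not stated; the point is only that nothing rules it out.

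Finally, per-surgeon learning curves are already planned, so case order may well be recorded, and a sensitivity analysis could sit in an SAP that is not shown. That is fair for the analysis. It does not answer the allocation, which is a design matter that the protocol does fix, without reference to surgeon.

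**Conclusion.** The point holds as a worthwhile, low-cost improvement, not as a demonstrated bias. The protocol documents an R-SS series for two surgeons, uses three in the trial without stating their R-SS experience, and does not arrange allocation by surgeon although it names surgeon as a possible confounder. The stated comparisons of hospital stay and return to work do not adjust for surgeon.

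Under an equal split, and if exactly one surgeon lacks R-SS experience, about a third of the R-SS arm is affected. Neither condition is in the document, so that third is not an upper bound, and the effect on power cannot be estimated from the protocol. If all three surgeons were already experienced in R-SS, the learning part of the point disappears; the case for balancing surgeon across arms remains.

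**What to change.** **Study 2.**
- State each trial surgeon's R-SS experience at the start of randomisation.
- Name the operating surgeon for each woman before her envelope is opened.
- Prepare a separate sealed series per surgeon, each balanced between arms (for example in permuted blocks), so that every surgeon operates in both arms.

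**Statistics.**
- Include surgeon in the primary comparisons, with hospital stay and return to work among them.
- Record each surgeon's cumulative R-SS case number, counting cases done before the trial.
- Prespecify a sensitivity analysis of the primary outcomes by surgeon and R-SS case order. One form excludes both arms' cases of a surgeon during that surgeon's early R-SS cases, with the cut-off fixed in advance. Read it for the size of the estimate: if all of one surgeon's cases dropped out under an equal split, about 62 − 21 = 41 women per arm would remain.

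**Dates.** Reconcile the two Study 1 periods with the May 2018 start of Study 2, and say whether the R-SS series closes before the first randomisation.

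**Cost.** Three envelope series instead of one, possibly one extra recorded variable, and less freedom in scheduling. The sample size does not change.
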